**Table 26: Definition of Terms for the Statistical Analysis**

Term	Definition
Baseline Value	The subject's last assessment prior to subject's first randomized product use in mCC/THS 2.2 Menthol arms. In the SA arm, the subject's last assessment prior to 10:00 AM on Day 1.

Where the baseline is different for any of the variables measured this will be specified in the relevant section.

In this SAP, references to the Day 30 Visit, Day 60 Visit and Day 90 Visit, Day 30, Day 60, and Day 90 refer to the nominal days.

Nominal Day 31 will be referred to as the second day of the Day 30 Visit. Nominal Day 61 will be referred to as the second day of the Day 60 Visit. Nominal Day 91 will be referred to as the second day of the Day 90 Visit.

For urine collections taken on Days x to y, e.g., Days 5 to 6, these will be referred to as collected on Day x, i.e. Day 5, in the SAP.

#### 12.1.5 Handling of Dropouts or Missing Data (including outside the limits of quantification)

For laboratory parameters:

- Values below the lower limit of quantification (LLOQ) will be imputed using LLOQ/2. For values above the upper limit of quantification (ULOQ), the ULOQ will be imputed.
- The number of values below LLOQ or above ULOQ will be presented in each summary table. If 50% or more data are below LLOQ or above ULOQ, only the number (%) of value below LLOQ or above ULOQ will be reported in the summaries, together with minimum and maximum of the observed values.
- Missing data at Baseline will not be imputed.

For BoExp:

- A last observation carried forward (LOCF) approach will be implemented to replace all missing data with the last available data for each parameter being assessed.
- For parameters assessed at several timepoints during a visit, the last available data at the timepoint being assessed collected at previous study visit will be used in the analyses. For example, if on Day 5, the evening assessment (20:00-23:00) is missing for COHb, the evening assessment from Day 4 will be used for analysis regardless whether other COHb assessments are available at Day 5.

For daily product use data in safety summaries:

- Product use categories will be defined based on percentage of THS 2.2 Menthol use calculated by averaging non missing consumption data over the entire ambulatory time interval.

For daily product use data in non-safety analyses and summaries:

- If at least 75% of the daily product use assessments over a period are available, with no more than 7-days of consecutive missing data:
  - Product use categories will be defined based on percentage of THS 2.2 use calculated by averaging non missing consumption data over the analysis interval.
  - Compliance to randomized product will be defined based on the available product use data.
- If less than 75% of the daily product use assessments over a period are available, or product use data is missing over a period of more than 7 consecutive days:
  - Product use categories will be defined based on percentage of THS 2.2 use calculated by considering the missing product use data as the CC use reported at Baseline.
  - Compliance to randomized product will be defined by considering the missing product use data as the CC use reported at Baseline.

For MNWS, QSU-brief, and MCEQ questionnaire data:

- Total scores and domain or subscale scores will be derived by averaging the individual non-missing item scores if at least 50% are non-missing, otherwise they will be set to missing.

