12.1.4 Handling of Missing Values and of Values Outside the Detection Limits

Missing values for the BoExp will be imputed using the last observation carried forward (LOCF) approach.

Values below the lower limit of quantification (LLOQ) will be imputed using 0.5 x LLOQ. For values above the upper limit of quantification (ULOQ), the ULOQ will be used for calculation and reporting in summary tables. The number of values below LLOQ or above ULOQ will be presented in each summary table.

Data and information contained in this document are considered to constitute trade secrets and confidential commercial information, and the legal protections provided to such trade secrets and confidential information are hereby claimed under the provisions of United States law. No part of this document may be publicly disclosed without the written consent of Philip Morris International.

For questionnaire data total scores and domain or subscale scores may use a certain degree of imputation by averaging across individual item scores.

Further details will be provided in the SAP.

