As the calculation of the sample size was based on the primary objective (reduction of Biomarkers levels in THS 2.2 Menthol relative to mCC), we assumed 50% of the subjects in the THS 2.2 Menthol arm would be using THS 2.2 Menthol exclusively and therefore will be included in the per-protocol population on Day 90.

In order to further optimize the assessment of BoExp and increase the comparability of the levels of biomarkers between THS 2.2 Menthol and SA the confounding effects of the use of any other tobacco or nicotine containing product (other than the assigned product) need to be controlled for. Therefore a subject will be considered abstinent based on the following categorization:

- “Abstinence”: 100% abstinence from tobacco or nicotine containing product use other than the assigned product

- Predominantly abstinent: not more than 0.5 uses of any tobacco or nicotine containing product (other than the assigned product) per day on average and no more than two uses on a single day occur.
- “Not abstinent”: more than 0.5 uses of any tobacco or nicotine containing product (other than the assigned product) per day on average or more than two uses on a single day occur.

The purpose of the defined threshold was to reduce the confounding effects of the use of any other tobacco or nicotine containing product (other than the assigned product). The results of a study PMI conducted in 2011 (PIPA_CEMA_01 study) to evaluate the capacity of the urinary biomarker CEMA to detect smoking of small amounts of CC use (down to 2 CCs) per day was used to help us identify this threshold. The results of this study show that CEMA used as a urinary biomarker of exposure to acrylonitrile is able to discriminate between non-smokers and smokers who have smoked only 2 CCs and 4 CCs with a maximum level of sensitivity and specificity at an optimal threshold of the 2.56 µg/L (CEMA Cmax in non-smokers) for CEMA and 3.76 µg/g for CEMA concentration adjusted for creatinine. For non-smokers CEMA and CEMA concentration adjusted for creatinine were greater than the LLOQ on only one occasion.

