### 12.6.1 Primary Analyses

#### 12.6.1.1 Analysis of Biomarkers of Exposure for Primary Endpoints

The BoExp (COHb in blood and urinary concentrations of MHBMA, 3-HPMA, S-PMA and Total NNAL) used for the primary analysis will be summarized as detailed in Section 12.1.3 “Descriptive Statistics”. The listing of the COHb data will have a flag for whether a subject’s COHb was <2%.

The baseline is as defined in Section 12.1.4 “Definitions for Statistical Data Analysis”.

The primary endpoints will be log-transformed (basee) prior to analysis. The analysis will compare the evening COHb level (20:00-21:30 PM) on Day 5; and urinary concentrations of MHBMA, 3-HPMA and S-PMA adjusted for creatinine on Day 5 and urinary concentrations of Total NNAL adjusted for creatinine on Day 90 Visit between the THS 2.2 Menthol and mCC arms for the PP Set. An analysis of covariance (ANCOVA) (Snedecor and Cochran 1982) model will be used with terms for the log-transformed baseline value, sex, average daily mCC consumption over the last 4 weeks as reported during screening and randomization arm.

The SAS code to be used for the THS 2.2 Menthol and mCC data is shown below:

```
Proc glm data=_data_;
Class randomization_arm sex cigarette_cons;
Model log_biomarker = log_baseline sex cigarette_cons
randomization_arm;
Lsmean randomization_arm / pdiff =control('mCC') alpha=0.05 cl;
Run;
```

The least squares (LS) means and estimate of the difference and the 95% CI will be back-transformed. The geometric LS means for each randomization arm along with the ratio

(THS 2.2 Menthol : mCC), two-sided 95% CI and one-sided p-value will be presented in the tables. THS 2.2 menthol : mCC effects will be graphed in a forest plot.

All figures, summaries and analyses will be performed on the PP Set. Additional descriptive statistics will be provided within the secondary analysis.

The data will be presented in the below outputs:

TFL number	Title
FIGURES	
15.1.1.1	Forest Plot of Statistical Analysis of Biomarkers of Exposure on Day 5 and Day 90 – PP Set
15.1.1.2	Biomarkers of Exposure Geometric Mean and 95% CI – PP Set
TABLES	
15.2.3.1.1	Analysis of COHb, MHBMA, 3-HPMA, S-PMA and Total NNAL on Day 5/90 Visit for THS 2.2 Menthol versus mCC for the Primary Objective – PP Set
15.2.4.1.1	Descriptive Statistics of Blood COHb (%) – PP Set
15.2.4.1.1.1	Descriptive Statistics of Blood COHb (%) by Sex – PP Set

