#### 12.6.2.1 Analysis of Biomarkers of Exposure for Secondary Endpoints

The BoExp for the secondary endpoints are exhaled CO and total 1-OHP, Total NNN, 4-ABP, 1-NA, 2-NA, o-tol, CEMA, HEMA, B[a]P, HMPMA, S-BMA, Total NNAL and NEQ (all analysed from a 24-hour urine collection) at Day 5 and Day 90 will be described as reported in Section 12.1.3 "Descriptive Statistics". Urine parameters will be analyzed as concentrations adjusted for creatinine and the quantity excreted in urine over 24 hours. In addition the quantity excreted in urine over 24 hours for MHBMA, 3-HPMA, S-PMA and Total NNAL will also be presented as above.

All BoExp apart from CO breath test will be analyzed in the log scale.

BoExp will be analyzed using the same model described in Section 12.6.1.1 "Analysis of Biomarkers of Exposure for Primary Endpoints". No adjustment will be made for multiple comparisons. For all BoExp, if the results from the Day 5 analysis are significant (one-sided p-value  $\leq 0.025$ ) then the statistical significance will be evaluated for the results of the analysis at Day 90 values. LS means for each product along with the ratio (THS 2.2 Menthol : mCC) and 95% CI will be presented in the tables. Forest plots of the ratios and 95% CI will also be produced.

BoExp will also be examined to compare the reductions in THS 2.2 Menthol vs. SA using the same methodology as above for the PP Set. In addition, the sensitivity analyses described in Section 12.6.1.3 "Sensitivity Analysis" for the biomarkers of exposure for primary objectives will be repeated for the biomarkers of exposure for secondary objectives.

The data will be presented in the below outputs:

TFL number	Title
FIGURES	
15.1.1.2	Biomarkers of Exposure Geometric Mean and 95% CI – PP Set
15.1.1.4	Biomarkers of Exposure Geometric Mean and 95% CI – FAS
TABLES	
15.2.3.2	Analysis of COHb, MHBMA, 3-HPMA, S-PMA, and Total NNAL on Day 5/90 Visit versus mCC and SA for the Secondary Objective – PP Set.
15.2.3.3	Analysis of COHb, MHBMA, 3-HPMA, S-PMA, and Total NNAL on Day 5/90 Visit versus mCC and SA for the Secondary Objective – FAS.
15.2.3.4	Analysis of Additional Biomarkers of Exposure versus mCC and SA on Day 5/90 Visit – PP Set.
15.2.3.5	Analysis of Additional Biomarkers of Exposure versus mCC and SA on Day 5/90 Visit – FAS.
15.2.3.6	Sensitivity Analysis of Additional Biomarkers of Exposure versus mCC and SA using Mixed Model on Day 5/90 Visit – PP Set

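### SAP 12.1.5 withholds means when half or more of the values are below LLOQ, but the log-scale ANCOVA still reports ratios and CIs from LLOQ/2-substituted data; under heavy censoring the THS:SA ratio then depends on the assay limit

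*SAP*

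**What the plan says.** Protocol 12.1.4 and SAP 12.1.5 use the same substitution: "Values below the lower limit of quantification (LLOQ) will be imputed using 0.5 x LLOQ" and "Values below the lower limit of quantification (LLOQ) will be imputed using LLOQ/2". SAP 12.1.5 adds a threshold: "If 50% or more data are below LLOQ or above ULOQ, only the number (%) of value below LLOQ or above ULOQ will be reported". The rule is worded for the summary tables, which also keep the lowest and highest observed value. It does not say whether the 50% is counted per arm, per visit or pooled.

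The model text has no matching condition. SAP 12.6.1.1 log-transforms the primary endpoints and fits "Model log_biomarker = log_baseline sex cigarette_cons" plus randomization arm. It then presents geometric LS means, the THS:mCC ratio, a two-sided 95% CI and a one-sided p-value. SAP 12.6.2.1 applies the same model to the secondary biomarkers of exposure (BoExp), on the log scale except for exhaled CO, and adds the abstinence arm: "BoExp will also be examined to compare the reductions in THS 2.2 Menthol vs. SA using the same methodology as above for the PP Set".

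The sensitivity analyses in SAP 12.6.1.3 remove the LOCF imputation and out-of-window data, or restrict to the compliant population. None changes the treatment of values below LLOQ.

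Protocol 12.5.4 says model assumptions will be tested, and that clearly non-lognormal BoExp data will be transformed or analysed non-parametrically. SAP 12.6 does not repeat this, and SAP Section 9 does not list it as withdrawn.

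**The concern.** The SAP distinguishes summaries from analyses, so a marker whose geometric mean is judged unfit to print in one table can appear in another with a geometric LS mean, a ratio and a CI. Where the authors wanted LLOQ to block an estimate they said so: SAP 7.1.3 and 7.1.4 do not calculate the CYP1A2 and CYP2A6 ratios when a component is at LLOQ. There is no equivalent for BoExp.

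By SAP 7.1.1 a substituted urinary value enters the model as (LLOQ/2)/creatinine or (LLOQ/2) × urine volume. It is not one constant, but its variation between subjects reflects urine dilution and not exposure.

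THS versus SA is the comparison at stake. Protocol 4.2 uses abstinence as the reference point for the largest achievable reduction, so low values are most likely in the arm that anchors interpretation. As both arms sink below LLOQ their substituted means converge. The ratio moves towards 1 and THS looks closer to abstinence than it is.

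**Working it through.** **Check of the scale against the plan's own figure.** Log-scale SD σ = √ln(1 + CV²); distance to the margin δ = ln(0.50/MR); SE = σ√(1/n₁ + 1/n₂); one-sided 2.5%. Under the first assumption set (SAP Tables 16, 17 and 19):

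- COHb (0.40, CV 0.32, 80:40): σ = 0.312, SE = 0.0605, δ = 0.223, power 0.958.
- Total NNAL (0.30, CV 0.60, 40:40): σ = 0.5545, SE = 0.124, δ = 0.511, power 0.985.
- The other three are essentially 1.

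The product is 94.3%, against 94% in SAP Table 20 (50% column). The second set gives 98.2% against 98%. The design ratios and CVs are therefore being read as the plan reads them.

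**Effect of substitution.** Let the log values be normal with mean μ and SD σ, let L = ln(LLOQ), z = (L − μ)/σ and p = Φ(z). The mean after replacing values below LLOQ with LLOQ/2 is

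p(L + ln 0.5) + (1 − p)μ + σφ(z).

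Set μ = 0 in the THS arm and μ = −ln(MR) in the comparator. Choose L so that an assumed 50%, 70% or 90% of THS values fall below LLOQ. These shares are assumptions, because the documents give none.

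**3-HPMA, THS:SA** (SAP Table 16: MR 1.70, CV 0.33, so σ = 0.3215 and the SA mean is −0.5306). At 50%, L = 0:

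- THS: 0.5 × (−0.6931) + 0.3215 × 0.3989 = −0.218.
- SA: z = 1.650, p = 0.951, giving 0.951 × (−0.6931) + 0.049 × (−0.5306) + 0.3215 × 0.102 = −0.652.
- Ratio: exp(0.434) = 1.54.

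| THS below LLOQ | SA below LLOQ | THS:SA with LLOQ/2 (true 1.70) | 95% CI coverage | THS:SA with LLOQ in place of LLOQ/2 |
|---|---|---|---|---|
| 50% | 95% | 1.54 | 84% | 1.13 |
| 70% | 98.5% | 1.29 | 1% | 1.06 |
| 90% | 99.8% | 1.09 | 0% | 1.02 |

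Coverage comes from 4,000 simulated trials per row with 80:40 subjects. The last column changes only the substituted constant, and at 50% that alone moves the ratio from 1.54 to 1.13.

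**S-PMA, THS:SA** (true 1.15, CV 0.42) is affected less: 1.17, 1.12 and 1.05, with coverage 96%, 95% and 48%.

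**Primary THS:mCC ratios with LLOQ/2**, by the same formula:

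| Marker (true ratio, CV) | 50% | 70% | 90% |
|---|---|---|---|
| MHBMA (0.15, 0.70) | 0.14 | 0.15 | 0.19 |
| S-PMA (0.20, 0.70) | 0.18 | 0.20 | 0.26 |
| 3-HPMA (0.30, 0.50) | 0.26 | 0.26 | 0.32 |
| COHb (0.40, 0.32) | 0.32 | 0.31 | 0.33 |
| Total NNAL (0.30, 0.60) | 0.27 | 0.28 | 0.36 |

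The highest is Total NNAL at 90%. In simulation its SE was 0.919 of the uncensored one: 0.919 × 0.124 = 0.114, so the upper limit is about 0.361 × exp(1.98 × 0.114) = 0.45, still below 0.50. The intervals are not reliable, however. S-PMA coverage is 87%, 93% and 26%, and Total NNAL coverage is 85%, 91% and 65%.

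**Censored model.** A left-censored log-normal fit recovers the S-PMA THS:mCC ratio at 0.20 with 93–95% coverage, even with 90% of THS values below LLOQ.

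**Limits.** The simulations have no baseline covariate and no creatinine or volume variation.

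**The case against.** **Protocol 12.5.4 already provides a fallback.** Protocol 12.6.4 refers the secondary BoExp back to it, and the SAP is written to supplement the protocol. So the statement that the ANCOVA would be run regardless rests partly on the SAP's silence. This stands as a qualification. But the provision has no trigger and names no method, and no transformation repairs a block of substituted values.

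**Heavy censoring is not established.** This also stands. The only evidence is Protocol 12.3: "For non-smokers CEMA and CEMA concentration adjusted for creatinine were greater than the LLOQ on only one occasion". A reader might infer that Day 90 CEMA in the SA arm will be almost entirely substituted. The documents do not support that. The remark concerns non-smokers in another study, whereas the SA arm consists of smokers asked to abstain. SAP Table 21 keeps in the PP Set those who average no more than 0.5 CC per day and never exceed two in a day. The same protocol paragraph says CEMA separates non-smokers from people who smoked only two cigarettes.

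**The trial's success does not depend on THS:SA.** Correct: SAP 5.5.2 rests on THS versus mCC alone. A reader might infer that substitution could produce or remove a success claim. At the design ratios it does neither in the scenarios above. A true ratio near 0.50 was not examined.

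**Readers can see the censoring.** SAP 12.1.5 puts the count outside the limits in each summary table and keeps the minimum and maximum. That helps, but the ratio and CI appear in separate analysis tables.

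**Conclusion.** The gap is real and conditional. The 50% rule stops at the summaries, the models use the LLOQ/2 values without any condition, and no planned sensitivity analysis tests that choice. If most values in both arms of a THS:SA contrast are below LLOQ, the ratio and its CI depend on the assay limit and the substituted constant. For 3-HPMA a true 1.70 becomes 1.29 at 70% and 1.09 at 90% of THS values below LLOQ, with almost no coverage. Near 50% the bias is moderate (1.54), and for S-PMA it is small until censoring is extreme.

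This rests on assumed shares below LLOQ, log-normal data and the design ratios and CVs in SAP Tables 16 and 17. It bears on secondary comparisons and does not call the primary success criterion into question. The change is worth making because the SAP itself foresees half or more of the values lying below LLOQ.

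**What to change.** 1. In SAP 12.6.1.3 and 12.6.2.1, for any BoExp with values below LLOQ at the analysed visit, add a pre-specified sensitivity analysis: a left-censored log-normal model (PROC LIFEREG or NLMIXED) with the ANCOVA covariates and subject-specific censoring limits. The limit is LLOQ/creatinine for the adjusted concentration and LLOQ × volume for the quantity excreted.
2. For THS:SA contrasts only, when 50% or more of the values in both arms are below LLOQ at that visit, report the proportions below LLOQ and no ratio or CI. This also fixes the denominator for these contrasts as per arm and per visit.
3. Do not apply suppression to the primary THS:mCC tests. A THS arm mostly below LLOQ would be strong evidence of reduction, and withholding that test would leave the criterion requiring all five endpoints impossible to evaluate.

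The cost is SAP wording and one more standard model, with no new data. Some THS:SA ratios would go unreported.

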4.2 Rationale for Study Design and Control Groups

The minimum age of 22 years in the inclusion criteria was selected based on:

- The legal age of smoking in the location of the chosen sites is 19 years.
- To account for the 3 years of smoking history.

This clinical study aims to demonstrate reductions in exposure to selected HPHCs in apparently healthy smokers switching to the THS 2.2 Menthol, a candidate MRTP, as compared to using mCCs (see IB Edition 2). The main reference in this study will be smokers who continue to smoke mCC. Smokers who stop smoking (the SA arm) will be used as a reference point for the maximum possible reduction in exposure to HPHCs.

The confinement period will provide information on maximum possible exposure reductions in a well-controlled environment and will allow full control of daily cigarette consumption. The ambulatory period will provide a perspective of product usage in the real world setting, where smoking of a few CC (menthol and non-menthol) in addition to THS 2.2 Menthol and SA is expected. It will provide information on reduction in selected BoExp and related changes in selected risk markers when THS 2.2 Menthol is used in a real world setting.

The choice of HPHCs to be assessed in this study is derived from the World Health Organization (WHO) (Ashley et al., 2008) and the draft guidance on Reporting Harmful and Potentially Harmful Constituents in Tobacco Products and Tobacco Smoke (FDA, 2011).

In the WHO list, 9 HPHCs (acrolein, CO, 1-3 butadiene, benzene, NNN, NNK, acetaldehyde, benzo[a]pyrene, and formaldehyde) with evidence of carcinogenicity, respiratory and cardiac

Data and information contained in this document are considered to constitute trade secrets and confidential commercial information, and the legal protections provided to such trade secrets and confidential information are hereby claimed under the provisions of United States law. No part of this document may be publicly disclosed without the written consent of Philip Morris International.

toxicity were recommended to be measured as priority in the smoke chemistry for mandated lowering (Ashley et al., 2008).

Exposure to 4 HPHCs (acrolein, CO, 1,3-butadiene, and benzene) among these 9 priority HPHCs will be assessed by measuring their respective BoExp as primary endpoints after 5 days of exclusive use of THS 2.2 Menthol, mCC or SA. The following characteristics apply to these primary BoExp:

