### **10.1 Full Analysis Set**

The FAS consists of all the randomized subjects who had at least one post-randomization product use experience, if randomized to THS 2.2 Menthol or mCC, and have at least one valid non-safety assessment (THS 2.2 Menthol, mCC, and SA arms).

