**For missing or partial dates:**

- Missing dates for Day 30, 60, and Day 90 Visits will be imputed for the calculation of product use exposure within periods by adding 30, 60, or 90 days to the randomization date. If the imputed date falls after discharge date (e.g. for early terminated subjects), then the discharge date will be used.
- Missing or Partial dates will not be imputed for Adverse Events (AEs), for medical history, and for concomitant medications, but assumptions will be made as follows to assign them to specific analysis categories:

Date information (*)	AE Category	Disease Category	Medication Category
Missing date or Partial date, (e.g., --May2012, or ---2011) if month/year is the same as, or later than the month and/or year of Screening.	Product-emergent	Concomitant disease	Concomitant medication
Partial date, (e.g., --May2012, or ---2011). If month and/or year is earlier than the month and/or year of Screening.	Not product-emergent	Medical history	Prior medication

(\*) Missing or partial date refers to stop date for disease and medication categories

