### 12.6.1.3 Sensitivity Analysis

As a sensitivity analysis, the ANCOVA model described in Section 12.6.1.1 "Analysis of Biomarkers of Exposure for Primary Endpoints" will be repeated for the PP Set at Day 5 and Day 90 data by means of a mixed model approach, without the LOCF data imputation described in Section 12.1.5 "Handling of Dropouts or Missing Data (including outside the limits of quantification)". Any data outside of the allowed time window (see Table 23: Assessment Windows) on Days 5 and 90 will be excluded from the analysis.

The SAS code to be used for the THS 2.2 Menthol and mCC data is shown below:

```
Proc mixed data=_data_;
  Class randomization_arm sex cigarette_cons;
  Model log_biomarker = log_baseline sex cigarette_cons
  randomization_arm;
  Lsmean randomization_arm / pdiff =control('mCC') alpha=0.05 cl;
  Run;
```

An additional sensitivity analysis will be produced for the primary analysis, summaries and graphs of the COHb, MHBMA, 3-HPMA, S-PMA and Total NNAL will be repeated for the compliant population for THS 2.2 Menthol vs mCC. The analysis will use the same model as described in Section 12.6.1.1 "Analysis of Biomarkers of Exposure for Primary Endpoints"

The data will be presented in the below outputs:

TFL number	Title
FIGURES	
15.1.1.3	Biomarkers of Exposure Geometric Mean and 95% CI – Compliant Population
TABLES	
15.2.3.1.2	Sensitivity Analysis of COHb, MHBMA, 3-HPMA, S-PMA and Total NNAL on Day 5/90 Visit for THS 2.2 Menthol versus mCC for the Primary Objective using Mixed Model – PP Set
15.2.3.1.3	Sensitivity Analysis of COHb, MHBMA, 3-HPMA, S-PMA and Total NNAL on Day 5/90 Visit for THS 2.2 Menthol versus mCC for the Primary Objective – Compliant Population
15.2.4.1.3	Descriptive Statistics of Blood COHb (%) – Compliant Population
15.2.4.2.3	Descriptive Statistics of MHBMA in 24-hour Urine Collection – Compliant Population
15.2.4.3.3	Descriptive Statistics of 3-HPMA in 24-hour Urine Collection – Compliant Population
15.2.4.4.3	Descriptive Statistics of S-PMA in 24-hour Urine Collection – Compliant Population
15.2.4.5.3	Descriptive Statistics of Total NNAL in 24-hour Urine Collection – Compliant Population

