### 12.6.2 Secondary Analyses

The analysis of COHb, MHBMA, 3-HPMA, and S-PMA at Day 90 and Total NNAL at Day 5 will be repeated for the PP Set.

The analysis of the COHb, MHBMA, 3-HPMA, S-PMA at Day 5/ Day 90 and Total NNAL at Day 90 will be repeated for the FAS as described in Section 12.6.1.1 "Analysis of Biomarkers of Exposure for Primary Endpoints". These endpoints will also be examined to compare the reductions in THS 2.2 Menthol vs. SA using the same methodology as for the primary analysis for the PP Set.

The baseline is for the biomarkers measured in urine is as defined in Section 12.1.4 "Definitions for Statistical Data Analysis".

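### LOCF with no stop at Day 6 lets confinement values of MHBMA, 3-HPMA and S-PMA stand as Day 90 values in the supplemental FAS analysis, and no planned FAS analysis shows the effect

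*SAP*

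**What the plan says.** Protocol 12.1.4 sets the rule: "Missing values for the BoExp will be imputed using the last observation carried forward (LOCF) approach". SAP 12.1.5 follows it, with an approach "implemented to replace all missing data with the last available data for each parameter being assessed". Neither text limits the carry-forward by period or setting.

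SAP 10.1 admits to the FAS randomized subjects with post-randomization product use (in the two product arms) who "have at least one valid non-safety assessment (THS 2.2 Menthol, mCC, and SA arms"). No Day 90 value is needed. SAP 12.6.2 states that the analysis of COHb, MHBMA, 3-HPMA, "S-PMA at Day 5/ Day 90 and Total NNAL at Day 90 will be repeated for the FAS", using the primary model.

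The analysis without carry-forward is specified in SAP 12.6.1.3 "for the PP Set at Day 5 and Day 90 data by means of a mixed model approach, without the LOCF data imputation". The other sensitivity analysis uses the compliant population, which SAP 10.4 defines as a subset of the PP Set. FAS Table 15.2.3.3 has no counterpart without LOCF.

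On the setting, Protocol 4.2 says: "The confinement period will provide information on maximum possible exposure reductions in a well-controlled environment". The same section expects some cigarette smoking in the THS arm once subjects are ambulatory. It also says that five days are enough for the short half-life markers to reach their lowest level.

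**The concern.** A Day 5 value and a Day 90 value answer different questions. On Day 5 the site hands out each stick; by Day 90 the subject has lived at home for weeks. If a subject leaves soon after discharge and goes back to cigarettes, a carried Day 5 value records the largest reduction the product can show in someone who is no longer using it. MHBMA, 3-HPMA and S-PMA have average half-lives of 24 hours or less (Protocol 4.2), so they follow current use closely.

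The stake is modest but real. SAP 8 allows for up to 50% of the THS arm (40 of 80) leaving the PP Set in the ambulatory period, mainly for non-compliance. The Day 90 FAS table is the planned THS:mCC biomarker estimate that keeps those subjects, so it should be possible to see how far it rests on confinement data.

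**Working it through.** **Which value is carried.** Protocol 7.5.1.3 and Appendix 1, Table A2 schedule 24-hour urine on Days 0 to 5 and then only at the Day 30, 60 and 90 Visits. The early-termination list in Protocol 9.5 has no biomarker urine. Appendix 1, footnote y calls for the Day 6 examinations at early termination, but the 24-hour urine row has no Day 6 dot, and Protocol 7.7.2 says a dot marks the day a collection starts. The last urine value of a subject lost between Day 6 and the Day 30 Visit is therefore Day 5, or the last earlier day observed. Later dropouts carry an ambulatory value.

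**The plan's own figure.** The documents give no dropout rate and no planned Day 90 FAS ratio to reproduce. The planning ratios can be checked through the stated power. With log-scale SD = √ln(1+CV²), one-sided 2.5%, n 80:40 (Total NNAL 40:40) and the product of five powers, joint power at the 50% criterion is 94.3% and 98.2%, against 94% and 98% stated. Nothing below depends on power.

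**Illustration of size.** Inputs: s = planning ratio THS:mCC from Protocol Table 19 (SAP Table 16), namely MHBMA 0.15, S-PMA 0.20, 3-HPMA 0.30; 80 THS subjects. Assumed: d = share of the THS arm lost between Day 6 and the Day 30 Visit; p = share of those who return to ratio 1; everyone else at s; carried Day 5 value at s; carry-forward in the mCC arm neutral.

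- LOCF ratio = s^(1−d) × s^d = s
- Actual ratio = s^(1−dp)
- Gap = 100 × (s^(1−dp) − s) percentage points

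Example, 3-HPMA, d = 0.10, p = 1: 0.30^0.90 = 0.338, gap 3.8. With d = 0.05, p = 0.5: 0.30^0.975 = 0.309, gap 0.9.

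| Early loss, relapse | MHBMA | S-PMA | 3-HPMA |
|---|---|---|---|
| 5% (4 of 80), half | 0.7 | 0.8 | 0.9 |
| 5%, all | 1.5 | 1.7 | 1.9 |
| 10% (8 of 80), half | 1.5 | 1.7 | 1.9 |
| 10%, all | 3.1 | 3.5 | 3.8 |
| any loss, none | 0 | 0 | 0 |

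With the Protocol Table 21 ratios (0.11, 0.07, 0.28) the gaps are 0.6/0.5/0.9 at 5% with half relapsing and 2.7/2.1/3.8 at 10% with all relapsing.

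**Two checks on the assumptions (10%, all relapse).** If 10% of mCC subjects also carry Day 5 values that are f = 0.8 to 1.25 times their Day 90 values, the LOCF ratio is s/f^0.10 and the gaps are 2.8–3.5, 3.0–3.9 and 3.2–4.5. If half of THS completers had an assumed ratio of 0.50, completers average c = √(0.50 × s) = 0.274/0.316/0.387. LOCF then gives c^0.9 × s^0.1 = 0.258/0.302/0.378 against an actual c^0.9 = 0.312/0.355/0.426, gaps of 5.4/5.3/4.8.

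**What a complete-case repeat would show.** The SAP 12.6.1.3 code has one record per subject and no repeated or random term, so dropping LOCF simply drops subjects without a Day 90 value. In the base illustration it returns s, the same as LOCF, and shows none of the gap. In the completer check it returns c, a shift of 1.6/1.4/1.0 points, about 20 to 30% of the gap.

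**The case against.** The strongest reply is that little hangs on this. The Protocol synopsis makes the FAS supplemental for biomarkers. SAP 5.5.2 applies the 50% criterion to these three markers on Day 5 only. SAP 10 says the aim is the optimal effect in compliant subjects and leaves real-world effects to other studies. All of that stands and keeps the point small. It does not explain why a confinement value should represent Day 90 in a table the plan chose to produce.

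Second, the affected group is narrow. Protocol 4.1 and 5.1.3 do not withdraw subjects for ambulatory smoking, so those who resume are meant to stay and give their own urine. This stands. A reader might infer that early leavers are mostly relapsers; the documents do not say so.

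Third, a reader might infer that the affected number is hidden. It is not. SAP 12.1.3 plans missing-data counts, SAP 12.2 plans visit completion and discontinuation reasons, and individual biomarker values are listed. The number can be worked out; it is just not reported directly, and no alternative FAS contrast accompanies it.

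Fourth, the same section treats long diary gaps the opposite way: "Compliance to randomized product will be defined by considering the missing product use data as the CC use reported at Baseline". It is tempting to call this a contradiction, but it is only an analogy. That rule concerns product use, and for missing visit dates SAP 12.1.5 adds: "If the imputed date falls after discharge date (e.g. for early terminated subjects), then the discharge date will be used". The period can therefore end when the subject leaves.

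Fifth, the direction does not extend to every marker. Total NNAL has a half-life of 10 to 15 days, so a carried Day 5 value still holds much of the baseline exposure and would tend to understate the reduction. COHb has its own time-point rule. Both, and the THS:SA comparison, are outside this point.

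**Conclusion.** The gap is real, narrow and optional to fix. As written, the plan enters confinement values of MHBMA, 3-HPMA and S-PMA as Day 90 values for THS subjects lost between Day 6 and the Day 30 Visit. No planned FAS analysis shows what that does. The direction favours THS only to the extent that those subjects resume smoking.

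The size cannot be known from the documents. The range of 0 to 3.8 points, or up to 5.4 with the assumed poorer completers, rests on assumed early loss of 5 to 10%, assumed relapse and roughly neutral carry-forward in the mCC arm.

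Two stronger readings are not supported. One is that the primary result or the success criterion is inflated: for these markers both sit on Day 5 in the PP Set, before any carry past Day 6 can occur. The other is that LOCF moves the Day 90 FAS result across a 50% reduction. The highest actual ratio in the scenarios above is 0.43. At the Table 19 ratios, with every leaver relapsing, reaching 0.50 needs early loss of 1 − ln 0.50/ln s: about 42% for 3-HPMA, 57% for S-PMA and 64% for MHBMA. Smaller losses suffice only if completers are also assumed to do much worse than planned, and no Day 90 threshold applies to these markers in any case.

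**What to change.** Keep the protocol-specified LOCF analysis. In SAP 12.6.2 add one Day 90 FAS sensitivity analysis for MHBMA, 3-HPMA and S-PMA. Confinement values are not carried past Day 6, and subjects with no ambulatory value, in both the THS and the mCC arm, are set to their own baseline value. Ambulatory values are still carried for later dropouts. Label it a conservative return-to-baseline scenario, not an estimate or a bound, since no text says that every leaver relapses.

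Report, by arm, how many subjects have a carried confinement value as their Day 90 FAS value. A complete-case FAS repeat may be added, with a note that it drops these subjects and so shows part of the effect or none.

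SAP 9 records that the study team was accidentally unblinded. Enter these there as added sensitivity analyses that replace nothing. The cost is a few tables, one count and a Section 9 entry. FAS reductions for these three markers may look slightly less favourable.
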